to examining the relationship between game performance and cognitive status, requiring a moderate number of participants. Thus, this study, designed with a statistical power of 0.8, an alpha level of 0.05, and a medium effect size of 0.7, requires a minimum sample size of 58 participants. Twenty-nine older adults (65 and above) who meet the diagnostic criteria for MCI, and 29 older adults with typical cognition will be eligible to participate in the study. Other reasons for justifying the sample size include: 1) The statistical analyses to answer questions that aim to compare two conditions, or two groups requires a smaller sample size; and this small sample size is insufficient to justify correlational analysis. 2) the "Events Per Variable" (EPV) rule is often used in statistical modeling, particularly in logistic regression, to determine the minimum sample size needed to ensure reliable and valid results. The general rule is to have at least 10 events (outcomes of interest) for each predictor variable (151). Therefore, using regression analysis to explore the six associated factors (game performance, age, sex, educational level, tech savviness, and living status) with the presence of MCI would necessitate 60 events (instances of the outcome of interest). Assuming an equal distribution of events and non-events, at least 120 participants would be needed in total to achieve 60 events, ensuring that each predictor variable is adequately supported by the data and enhancing the reliability of the statistical model. However, for a feasibility study involving a brand-new, untested test, it is not ethical to recruit a large sample size and burden vulnerable older adults with participation. Besides, at this point of the study, it is not known how many independent variables will be included in the model and that depends on the results of the factorial analysis that precedes the logistic model. Therefore, I aim to treat the research about the associated factors with the presence of MCI (RQ4) as a pilot to gather preliminary data. This approach can help refine the research design and hypotheses, and the results can be used to justify the need for a larger study

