3.6 Variables

The study variables are the following:

- Game performance collected through various game metrics, including total time of
 playing, the ability to complete the whole game, the ability to manage the budget, number
 of errors, the number of checking the shopping list, and the game performance accuracy.
 - Total Time of playing: This numerical variable refers to the total time that takes to complete all 6 stages in seconds with the maximum of 1800 seconds.
 - The ability to complete the game: This binary variable (1= Could complete, 0= Could not complete) refers to the participant's ability to complete all the 6 stages of the game.
 - The ability to manage the budget: This binary variable (1 = Could manage, 0 =
 Could not manage) refers to the participant's ability to keep their purchases equal to or below the budget limit provided for each level.
 - The number of errors: This numerical variable refers to the total number of mistakes made by participants, including mistaken, missed, and repeated items purchased.
 - The number of times the participant opens up the reading list: This numerical variable refers to the total number of times the participant open and check the shopping list within the 6 stages.
 - O The game accuracy: This numerical variable represents the success in the game, ranging from 0 to 100, where higher values mean higher game performance.

Demographics

 Age (In number of years): It refers to the chronological age of an individual in years at the time of data collection. This variable is considered as numerical in this study.

- Sex at birth: It refers to sex assigned at birth. Categories for this variable are male and female.
- Level of education: It refers to the highest degree or level of school completed by the participants. Categories for this variable are elementary school, high school, bachelor's degree, master's degree, and higher.
- Technology savvy: This categorical refers to the familiarity and experience of the
 participants with technology. It will be collected and measured based on the
 number of technological devices they use and the frequency of their usage.
- Living status: It refers to the participants' living condition. Categories for this
 variable are living alone, living with family, and living in an institution

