Finally, the ROC curve will be calculated and plotted. TPR and FPR need to be calculated for various threshold values. Then, TPR (y-axis) against FPR (x-axis) for each threshold will be plotted. The closer the ROC curve is to the upper left corner, the higher the test's accuracy, as this position represents a sensitivity of 1 and a false positive rate of 0 (specificity of 1). An ideal ROC curve has an AUC of 1.0. An AUC of 0.5 indicates no discrimination, 0.7 to 0.8 is acceptable, 0.8 to 0.9 is excellent, and above 0.9 is considered outstanding (155,156).

To investigate if the game performance is an associated factor with cognitive status controlled by demographic variables (RQ4), logistic regression analysis (157) will be used. For all variables, categories will be combined into broader categories, when possible, to improve the power of the logistic regression model (158). Chi-Square test will be used to determine if there is a significant

association between variables and cognitive status. Principal Component Analysis (PCA) will be used to reduce the number of variables in a dataset while preserving as much variability (information) as possible (159). To determines which factors to retain based on explained variance, and Eigenvalue Cut-Off of 1 will be applied. Following this, logistic regression model will be run with the included variables. The performance of the logistic regression model with be evaluated using ROC analysis and test characteristics (160).

To compare the differences between the level of anxiety while playing the game and while traditional cognitive tests in older adults with typical cognition and with MCI (RQ5), either the Paired t-test or Wilcoxon Signed-Ranks test (155) will be used as appropriate, with an α level of 0.05, to compare the anxiety level in the two conditions- while playing the games and while performing MoCA. If the mean difference is significant and lower while playing the game compared with MoCA and Qmci, it means that the G3 causes less anxiety compared to the traditional cognitive screening tools.

To explore the usability of the game-based screening (RQ6), the SUS results will be calculated and interpreted as follows:

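### The 60-event, 120-participant benchmark holds only for one game score and single-term factors, and the data-chosen RQ4 model is then judged by ROC on the same 58 people

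*Protocol*

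**What the plan says.** Section 3.3 gives the rule: "The general rule is to have at least 10 events (outcomes of interest) for each predictor variable". It applies the rule to "six associated factors (game performance, age, sex, educational level, tech savviness, and living status", says that this "would necessitate 60 events (instances of the outcome of interest", and, with half the participants being events, that "at least 120 participants would be needed in total to achieve 60 events". It does not adopt that size. The planned sample is "Twenty-nine older adults (65 and above) who meet the diagnostic criteria for MCI, and 29 older adults with typical cognition", taken from a correlation calculation. The same section says that the number of independent variables is not yet known, treats RQ4 as a pilot, and intends a simpler model that keeps only the strongest predictors, judged from the data.

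Section 3.6 describes "Game performance collected through various game metrics" and lists six of them: total time, completion, budget management, errors, list checks and accuracy. Education has four categories, or five if the last entry is read as two. Living status has three. Technology savviness is categorical with no levels given. Age is numerical and sex has two categories.

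Section 3.9 (RQ4) merges categories where possible, screens variables with chi-square tests, applies PCA with an eigenvalue cut-off of 1, fits the logistic model, and then states: "The performance of the logistic regression model with be evaluated using ROC analysis and test characteristics". On the AUC scale in the same section, 0.7 to 0.8 is acceptable.

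**The concern.** The count of six in section 3.3 does not match the variables in section 3.6. A factor with k categories costs k − 1 coefficients, and six game metrics are one predictor only if they are first combined into one score. The shortfall that the protocol admits for RQ4 is therefore larger than it appears.

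The second part matters more for what will be reported. Reducing the model by picking the strongest predictors from the data does not remove the discarded candidates from the overfitting account. If the chosen model is then assessed by ROC on the people used to choose and fit it, the AUC is biased upward. A game with no discriminating ability could contribute to a model that lands in the protocol's own acceptable band.

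**Working it through.** **The protocol's figure.** Events = 10 × predictors; participants = events ÷ 0.5.
- 10 × 6 = 60 events; 60 ÷ 0.5 = 120 participants. Reproduced exactly.

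**Counting coefficients from section 3.6.** A numerical variable takes 1 term and a k-category factor takes k − 1. Assumptions: four education categories, and two technology levels, the fewest possible because none are stated.
- One game score: game 1 + age 1 + sex 1 + education 3 + technology 1 + living status 2 = 9 terms. This needs 90 events, 180 participants.
- All six metrics: 6 + 1 + 1 + 3 + 1 + 2 = 14 terms. This needs 140 events, 280 participants.

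**Sensitivity to the assumptions.**

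| Education categories | Technology levels | One game score: events / people | Six metrics: events / people |
|---|---|---|---|
| 4 | 2 | 90 / 180 | 140 / 280 |
| 4 | 3 | 100 / 200 | 150 / 300 |
| 4 | 4 | 110 / 220 | 160 / 320 |
| 5 | 2 | 100 / 200 | 150 / 300 |
| 5 | 3 | 110 / 220 | 160 / 320 |
| 5 | 4 | 120 / 240 | 170 / 340 |

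If every factor is merged to two levels, the five demographics take 5 terms. One game component then gives 6 terms (60 / 120), two give 7 (70 / 140), and all six metrics give 11 (110 / 220).

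**What 29 MCI cases support.** 29 ÷ 10 = 2.9, so two terms at the protocol's rule. Events per term are 29 ÷ 6 = 4.8 for six terms, 29 ÷ 9 = 3.2 for nine and 29 ÷ 14 = 2.1 for fourteen.

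**Optimism in the ROC evaluation.** Simulated studies of 29 versus 29 people used predictors unrelated to group, so the true AUC is 0.5. A logistic model was fitted and its AUC computed on the same data.

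| Model-building step | Mean apparent AUC | Share at 0.70 or more |
|---|---|---|
| Two predictors fixed in advance | 0.59 | about 3 to 4% |
| Best 3 of 11 candidates kept | about 0.70 | about 50% |
| PCA on 11 variables, eigenvalue above 1 | about 0.63 to 0.66 | about 10 to 26% |

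The 11 candidates are the six metrics and five demographics, each taken as one variable. The PCA rows assume that all 11 enter, that the demographics are independent, and that the game metrics are correlated with one another between 0 and 0.7. About 3.5 to 5 components are then retained.

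**The case against.** The protocol's arithmetic is right on its stated inputs, and its rule is worded per predictor variable, not per coefficient. With one game score, six variables is a correct count. Section 3.9 plans to merge categories and run PCA, so 60 / 120 can match the model eventually fitted. All of this stands, and it is why 90 / 180 and 140 / 280 are minima for the uncollapsed variables and not fixed replacements. However, merging is planned only where possible, and an eigenvalue cut-off does not fix the number of components. Section 3.3 itself leaves the number of variables open, so nothing ensures six terms.

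Three stronger readings are tempting, and the document does not support them.
- A reader might infer that 120 is proposed for the later study and is too small for it. Section 3.3 gives 120 as a reason for not sizing this study on regression; of the future it says only that the results may justify a larger study.
- A reader might infer that the planned 58 is undermined. It comes from a separate calculation, RQ4 is declared a pilot, and section 3.11 concedes that a more reliable regression model needs a larger sample.
- A reader might fit all raw variables to noise and quote the result: mean apparent AUC 0.75 with 11 predictors and 0.79 with 14, reaching 0.70 in 81% and 94% of studies. Those are not the planned models. The figures for selection and for PCA are the relevant ones, and they are smaller.

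It is also fair that validation detail often belongs in a statistical analysis plan, which may exist. But the protocol already fixes the sequence of selecting on the data and then evaluating by ROC, and it describes no second sample.

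**Conclusion.** The point holds in a limited form. The 60 / 120 benchmark is conditional on one game score and single-term factors, and section 3.3 does not say so. With the section 3.6 variables uncollapsed, the minima are 90 / 180 and 140 / 280, and more if education has five categories or technology savviness more than two levels. The effect is to understate an acknowledged shortfall in a pilot objective; no sample-size decision changes.

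The consequence for reporting is the upward bias in the RQ4 model's AUC, which remains under each simplifying step tested. Its size depends on which step dominates: a mean of about 0.70 from noise if the best 3 of 11 are kept, and about 0.63 to 0.66 if PCA alone sets the model. Keeping three predictors is an assumption, as the protocol gives no number, and the PCA range rests on the assumed correlations. The full sequence of screening, PCA and selection was not simulated as one.

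**What to change.** In section 3.3, state that 60 events and 120 participants assume one game score and one term per factor. Give the minima for the uncollapsed variables: 90 / 180 with one game score and 140 / 280 with all six metrics, on four education categories and two technology levels.

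In section 3.9, limit the RQ4 pilot model to about two terms, chosen before the data are seen. If more demographic terms are kept, so that RQ4 still adjusts for demographics, fit a penalised (Firth) logistic model. In either case report the AUC, sensitivity and specificity after a bootstrap optimism correction that repeats the screening, PCA and selection steps in every resample.

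The cost is a few sentences and a little more analysis, with no extra participants. The downside is fewer freely estimated covariates and a less favourable reported AUC.

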3.4 Sampling strategy

The accessible population of older adults with MCI and typical cognition.

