Subsequent studies have broadened the symptoms of MCI to include other cognitive domains, leading to the development of the Petersen Criteria (62). Petersen criteria are characterized by a cognitive complaint, preferably confirmed by an informant, intact global cognition, unimpaired ADL, and absence of dementia, without significant disruption of iADL (62). However, subtle challenges in iADL might be evident (63). The Diagnostic and Statistical Manual of Mental Disorders 5th Edition (DSM-V) also characterizes MCI as a "mild neurocognitive disorder." It requires both subjective and objective cognitive decline compared to the prior level of cognitive abilities but is not defined as dementia or other psychological disorders (64). The prevalence of MCI varies widely, ranging from 0.5% to 41.8% (65), with an overall prevalence of 19.7% in the world (66). Risk increases with age, and men appear to be at higher risk than women (67). Additionally, lower educational level, vascular risk factors (e.g., diabetes and hypertension), Apolipoprotein E (APOE) e4 genotype, vitamin D deficiency, sleepdisordered breathing, and prior critical illness (e.g., sepsis) are other risk factors for MCI (68,69). Classification of MCI is challenging due to its heterogeneous nature. However, it could be classified based on either etiology or the existence of memory impairment (61). Based on etiology MCI is classified into 1. MCI associated with Alzheimer's Disease (AD) which is associated mostly with memory decline. However, it might affect other cognitive domains as well (70); 2. Vascular MCI (VMCI) is related to issues with blood vessels in the brain, affecting multiple cognitive functions (71); 3. MCI caused by Parkinson's Disease (PD-MCI) represents a transitional state between normal cognition and dementia in Parkinson's disease, affecting either memory or other cognitive domains or even both memory and other cognitive domains (72). MCI is also classified based on the presence of memory impairment. It is divided into amnestic

(aMCI), involving memory decline with or without other cognitive issues, and non-amnestic (non-aMCI), marked by impairments in cognitive areas other than memory (61).

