2.3.5 Serious Computer Games as screening tools for MCI

Only a handful of studies have applied SCGs for MCI screening, revealing significant differences in game performance between older adults with MCI and their healthy counterparts For instance, Zygouris et al. noted that individuals with MCI took significantly longer to complete games than their healthy counterparts (t = 4.84, p < 0.001) (139). Similarly, Gielis et al. observed distinct differences in 12 out of 23 digital biomarkers, including time-based, errorbased, and result-based metrics, highlighting substantial discrepancies between the two groups (140). Therefore, the SCGs could differentiate or classify older adults with and without MCI. However, more studies are needed to test more game scenarios and investigate the association of demographic factors with game performance in PwMCI and healthy counterparts. Research has also explored the criterion validity of the game-based screenings for MCI detection, highlighting significant correlations between game metrics and cognitive status (39,41,139–146). Numerous game metrics, including completion ability, gameplay duration, accuracy of actions, and total score, have been examined for their relationship with cognitive status. For instance, Zygouris et al. found a negative correlation (r= -0.2) between game playtime and cognitive test scores, suggesting that older adults with lower cognitive status required more time to complete games (139). Zygouris et al. also found correlations between education (r= -0.3 and r = -0.23) and age (r = 0.2 and r = 0.24) with the total time needed to complete the game (22,139). It means that a higher education level is associated with faster game completion, while older age correlates with longer completion times. Cabinio et al. found a correlation between game performance accuracy, reaction time, total playing score and cognitive status in PwMCI and the comparison group (43). Although these findings affirm the criterion validity of gamebased screenings, the correlations are not strong. Only one study explored the correlation of the

demographic variables and the game performance. Further research is necessary to clarify the relationships between traditional cognitive screening scores and various game metrics, evaluating the validity of game-based screenings.

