3.2 Participants

3.2.1 Inclusion criteria

- Older adults who are aged 65 and above with typical cognition or MCI as reported by themselves, or a health care professional.
- Older adults participating in this study must have MoCA score of 18 or higher.
- Older adults participating in the study must have functional vision and hearing, with or without aids such as glasses or hearing aids that enable them to interact with the game and comprehend the instructions. As part of the study recruitment activities, the researcher will explain the tasks required and discuss the vision and hearing demands.

- Older adults participating in the study must be capable of communicating and comprehending assessments, instructions, and simple sentences in English, as communication and comprehension is essential for interacting effectively with game components and the researcher. To assess their communication, reading, and comprehension skills, the researcher will provide participants with a few sentences in English related to the game content. Participants will be asked to read these sentences aloud and explain the meaning of the sentence to confirm their ability to read and understand the content.
- Older adults participating in the study must have adequate upper extremity function to play the game, using a mouse and do paper-and-pencil based measurements, using a pencil. During the study's introduction and training part of the game, potential participants can report any physical limitations. The researcher will also screen for these issues.

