3.5 Settings and Materials

3.5.1 Settings

The study will be conducted either in the spaces provided by the partner community organizations (e.g. assistive living facilities) or in Room 1-43 or 1-45 of the Corbett Hall, at the Faculty of Rehabilitation Medicine, University of Alberta.

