3.7 Recruitment

An email containing information about the study will be sent to partner organizations, including hospitals, memory clinics, day programs, assisted living facilities, retirement homes, and community groups. Additionally, flyers will be posted in various locations within the University of Alberta Medical Clinics, at community organizations that agree to support the study, and on social media platforms. The flyers will provide details about the research opportunity and the contact information of the researcher.

If an organization shows interest, an information session will be held to provide further details about the project and address any questions from the staff and potential participants. Older adults from these partner organizations who can provide informed consent and are interested in participating can directly contact the researcher to obtain more information or express their interest in participating. Individuals who see the flyer and contact the researcher can ask questions and receive more information through email, phone calls, or in-person or online meetings.

Interested older adults who meet the inclusion criteria will provide their contact information to the researcher to schedule an introductory session and a potential data collection session. During the introductory session, potential participants will learn about G3, its functionalities, and how to use the computer to play the game. The potential participant will be also asked to read some sentences aloud to ensure they can follow the instructions, read, and understand the content. The researcher will screen participants based on the inclusion and exclusion criteria, observing for any physical or communication difficulties that could negatively impact their engagement with

the game. Even if participants do not meet the inclusion criteria, they will still be allowed to play the game to maintain their dignity.

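### RQ3 reports G3's sensitivity, specificity, accuracy and AUC with no demographic benchmark, in two unbalanced volunteer groups, so part of the AUC may reflect age and schooling

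*Protocol*

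**What the plan says.** **Sampling.** Section 3.4 of the protocol is one incomplete sentence: "The accessible population of older adults with MCI and typical cognition". Section 3.7 recruits volunteers through partner organisations, "including hospitals, memory clinics, day programs, assisted living facilities, retirement homes, and community groups", and through flyers and social media. Section 3.2.1 applies one open-ended age rule to both groups: "Older adults who are aged 65 and above with typical cognition or MCI as reported by themselves, or a health care professional". Section 3.3 sets the numbers: "Twenty-nine older adults (65 and above) who meet the diagnostic criteria for MCI, and 29 older adults with typical cognition". No section mentions matching, stratification or balancing.

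**Age and education.** On MCI, section 2.2.1 says "Risk increases with age, and men appear to be at higher risk than women" and lists lower education among the other risk factors. On game time, section 2.3.5 cites correlations from earlier work and reads them as meaning that "a higher education level is associated with faster game completion, while older age correlates with longer completion times".

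**Analysis.** Section 3.3 names diagnostic accuracy as a primary objective. For RQ3, section 3.9 gives formulas for sensitivity, specificity and accuracy and describes the ROC curve and AUC. No covariate or demographic comparator appears there. Demographics enter the RQ1 MANCOVA and the RQ4 logistic model, which section 3.3 treats as a pilot.

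**The concern.** Age and education are tied by the protocol to both sides of the RQ3 comparison: to being in the MCI group and to how long a game takes. Total playing time is one of the six G3 metrics in section 3.6. If the MCI volunteers are older or less educated than the typical-cognition volunteers, a ROC curve on playing time will separate the groups to some extent for that reason alone. The RQ3 figures carry nothing by which a reader could see how much.

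This matters because section 3.9 fixes verbal grades for the AUC (0.7 to 0.8 acceptable, 0.8 to 0.9 excellent), and these would be attached to G3. The protocol also faults earlier work on this ground: sections 1.2 and 2.3.6 say demographics were often overlooked, and section 2.3.5 says their use in diagnostic-accuracy models is unexplored.

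**Working it through.** The protocol gives no figure for this effect, so there is none to reproduce. The calculation asks what AUC total time would show if G3 carried no information about MCI and the groups differed only in age and education.

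**Inputs from the protocol**
- Correlation of age with completion time: 0.2 and 0.24 (section 2.3.5; a different game).
- Correlation of education with completion time: -0.3 and -0.23 (same place). The sign is reversed below, so that less education means longer time.
- Group sizes: 29 and 29 (section 3.3).

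**Assumptions, not in the documents**
- The MCI group is *k* SD older and *k* SD less educated, with *k* from 0.5 to 1.0.
- Time is normal, and age and education are uncorrelated.
- The cited correlations hold within each group and carry over to G3.

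**Formula.** The shift in mean time, in within-group SDs, is s = k(r_age + r_edu), and AUC = Φ(s/√2). If the shift is scaled by the residual SD instead, s is divided by √(1 − r_age² − r_edu²). That variant is slightly larger and gives the upper end of the range. The smallest and largest coefficient pairs bound the result.

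| Pair (age, education) | k | s | AUC | s, residual SD | AUC |
|---|---|---|---|---|---|
| 0.20, 0.23 | 0.5 | 0.215 | 0.560 | 0.215/0.952 = 0.226 | 0.563 |
| 0.20, 0.23 | 1.0 | 0.430 | 0.619 | 0.430/0.952 = 0.451 | 0.625 |
| 0.24, 0.30 | 0.5 | 0.270 | 0.576 | 0.270/0.923 = 0.292 | 0.582 |
| 0.24, 0.30 | 1.0 | 0.540 | 0.649 | 0.540/0.923 = 0.585 | 0.660 |

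The range is therefore about 0.56 to 0.66. With balanced groups (k = 0) the AUC is 0.50.

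**Sensitivity of the result**
- *Age gap only:* 0.53 at 0.5 SD and 0.56 to 0.57 at 1.0 SD.
- *Coefficients paired in the order listed* (0.20 with 0.30; 0.24 with 0.23): 0.63 to 0.65 at 1.0 SD across the two scalings.
- *Overlap:* if age and low education correlate at an assumed 0.3, the joint shift s is divided by 1.3. The AUC is then 0.55 to 0.56 at 0.5 SD and 0.59 to 0.62 at 1.0 SD.
- *A real MCI effect:* a balanced-group AUC of 0.75 corresponds to a shift of √2 × Φ⁻¹(0.75) = 0.954. Adding 0.215 to 0.270 (0.5 SD gaps) gives an observed AUC of 0.80 to 0.81, at the protocol's boundary between acceptable and excellent. Adding 0.43 to 0.54 (1.0 SD gaps) gives 0.84 to 0.85.

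**Precision.** With 29 per group, the Hanley-McNeil standard error of the AUC is about 0.076 at 0.56 and 0.064 at 0.75 (95% half-width 1.96 × 0.064 = 0.13).

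**The case against.** **The study does look at demographics.** RQ4 asks whether game performance is associated with cognitive status after controlling for them, and its model is itself assessed by ROC; the RQ1 MANCOVA takes them as covariates. This stands against a reading that a reader might reach, namely that the study could not tell MCI detection from age and schooling. It does not supply what RQ3 lacks. The MANCOVA concerns group differences. The RQ4 ROC describes a model that mixes game and demographic variables after PCA, with 29 events against the 60 that section 3.3 says six predictors would need.

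**The correlations are borrowed.** They come from another game, cover completion time only, and are associations. Section 2.3.5 does not say whether they were computed within groups; if pooled, they may already contain MCI effect. RQ3 does not say which G3 metric feeds the ROC, and the documents give no age or education correlation for errors, budget or list checks. All of this stands. It supports a direction for time-based metrics but not a size for G3.

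**The gaps are chosen.** No expected gap is stated, and the upper figures need 1.0 SD on both factors at once. At 0.5 SD the shift of 0.06 to 0.08 is no larger than about one standard error of the AUC. This also stands.

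**Matching is debatable.** If MCI patients in the intended population really are older and less educated, unmatched groups reflect that case mix and matching would alter it. Three age bands by two education levels would make six cells for 29 volunteers. This stands against making matching a requirement.

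**ROC detail may belong in an analysis plan.** In general it may, but section 3.9 sets out the RQ3 analysis itself, so the benchmark belongs beside it.

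**Conclusion.** The point holds for RQ3 only. Its accuracy estimates come from two volunteer groups that nothing balances, with no demographic adjustment or benchmark, although the protocol links age and education both to MCI and to game time. Under the stated assumptions, the AUC for total time with no MCI effect would be about 0.56 to 0.66, or 30% to 80% of the way from 0.5 to the 0.7 that the protocol calls acceptable (0.06/0.20 to 0.16/0.20). It would be smaller with overlapping covariates or with correlations that include MCI effect, and absent if the groups turn out alike.

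Two stronger inferences are not supported. The documents do not show that the groups will differ by any given amount, so the figures illustrate a possible bias and do not predict one. Nor do they show that an unmatched sample is an error: for a first feasibility study it is a defensible choice, provided RQ3 shows what demographics alone achieve.

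**What to change.** In section 3.9, under RQ3:

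1. Report age and education by group.
2. Report the AUC of age plus education alone beside the G3 AUC.
3. Report the AUC gain, with its confidence interval, when G3 is added to age and education; an age- and education-adjusted ROC curve is an alternative.
4. Limit statements about G3's accuracy to what these results support.

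Age and education are already collected under section 3.6, so no participants, visits or procedures are added. The cost is one or two extra ROC analyses, with wide intervals at 29 per group.

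Frequency matching of the typical-cognition group on age band and education is optional. If it is adopted, the protocol should name the intended-use population, because matching changes the case mix, and should allow for slower filling of the cells.
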